Section	Original Text (Amendment 3.1, 21 December 2016)	Revised Text (Version 4, 10 May 2017)	Justification for Change
	
subject should also be assessed by Fibroscan® TE where available and progression to cirrhosis confirmed by biopsy unless not medically indicated. Sites participating in the paired biopsy sub-study (see Appendix C) must confirm progression to cirrhosis by biopsy.
	
criteria, the subject should also be assessed by Fibroscan® TE where available and progression to cirrhosis confirmed by biopsy (centrally read) unless not medically indicated. Laboratory samples needed to obtain noninvasive scores of liver fibrosis (ELF, and aspartate aminotransferase to platelet ratio index [APRI]) will also be collected when a subject develops evidence of progression to cirrhosis.
 
Full instructions concerning the sample collection methods, processing, labeling, and shipping will be provided by the Sponsor in a study-specific histology manual. Collection supplies will be provided by the central laboratory.
 
Sites participating in the paired biopsy substudy must confirm progression to cirrhosis by biopsy as per the information outlined in protocol Addendum 2.
	

Section 9.7.6 Screening Procedures
	
Two Screening visits will occur from 1 to 8 weeks prior to Day 0 (as outlined below) allowing for the collection of repeated serum chemistry samples (at least 2 weeks apart) to confirm pretreatment ALP and total bilirubin values:
 
Insertion
	
Collection of 2 serum chemistry samples (collected at least 2 weeks apart) during Screening is required for confirmation of the pretreatment serum chemistry values, including the ALP and total bilirubin used to determine eligibility:
 
 • When the 2 bilirubin or ALP assessments collected at Screening Visit 1 and Screening Visit 2 differ by $\geq 30\%$, a third sample must be collected at an unscheduled visit as a confirmatory sample to include in the mean result(s) that will be used to determine eligibility. 	
Allows repeat assessments when baseline laboratory values are discrepant between Screening Visit 1 and Screening Visit 2.

Section	Original Text (Amendment 3.1, 21 December 2016)	Revised Text (Version 4, 10 May 2017)	Justification for Change
	
 ...the dual-emission X-ray absorptiometry (DEXA) bone density scan to be done at Day 0 (selected study sites only), 
Insertion
	
 ...the dual-emission X-ray absorptiometry (DEXA) bone density scan to be done at Day 0 (at all study sites where the device is available), 
In the event that the 2 screening bilirubin or ALP assessments differ by $\geq 30\%$, and a third confirmatory sample is required to be collected, the Screening Visit window may be extended up to 3 additional weeks.
	

Section 9.7.8 Month 1 Procedures
 
Section 9.7.10 1-Month Post-Titration visit Procedures
	
Insertion (9.7.8)
 
Insertion (9.7.10)
	
 - A physical examination should be performed at the Month 3 visit if an onsite Month 1 visit was not performed. - A physical examination should be performed at the next scheduled visit if an onsite post-titration visit was not performed. 	
Clarification

Section 9.7.12 Month 9 Procedures
 
Section 9.7.14 Month 12 Procedures
 
Section 9.7.16 Month 16 Continued Follow-Up Procedures
 
Section 9.7.17 Month 12 Follow-up Procedures
 
Section 9.7.18 EOS/EOT
	
Section 9.7.12, 9.7.14, 9.7.16, 9.7.17, and 9.7.18
 
...DEXA procedure to be done at selected study sites only,
 
Section 9.7.14, and 9.7.17
 
 Perform an endoscopy (at selected study sites, where available) 	
Section 9.7.12, 9.7.14, 9.7.16, 9.7.17, and 9.7.18
 
...DEXA procedure to be done at all study sites where the device is available
 
Section 9.7.14, and 9.7.17
 
 Perform an endoscopy (at all study sites, where device is available) 	
Clarification

Section	Original Text (Amendment 3.1, 21 December 2016)	Revised Text (Version 4, 10 May 2017)	Justification for Change
Section 9.7.18 EOS/EOT	If the subject reports having eaten within 8 hours, document accordingly in the source and CRF and remind the subject that fasting is required prior to all study visits.	If the subject reports having eaten within 8 hours, document accordingly in the source and CRF.	Clarification
Section 10.3 Investigational Product Storage	The investigational product should be stored in the containers in which they are received from the Sponsor's supplier, at 15°C to 25°C.	All OCA tablet strengths provided to clinical trial sites in support of clinical study are to be shipped and stored at 15°C to 25°C. Temperature excursions within the range of 2°C and 30°C for no more than a 6-month period are acceptable, and the OCA tablet continues to be suitable for use in clinical studies. Additionally, temperature excursions within the range -20°C to 40°C for no more than 7 days are acceptable, and the OCA tablet continues to be suitable for use in clinical studies.	Updating temperature excursions language per Sponsor stability studies.
Section 11.1.2 Secondary Assessments	
Insertion
 
 • Histological assessment of disease progression or improvement using paired biopsies in a subset of subjects (defined in Appendix C). • Biomarkers, including other markers of hepatic fibrosis and/or inflammation, to be tested will include: IgM, c reactive protein (CRP), tumor necrosis factor α (TNF-α), FGF 19, cytokeratin-18 (CK-18) and ELF, (and others as determined during the course of the study). 	
 • Individual components of the primary endpoint. • Histological assessment of disease progression or improvement using paired biopsies in a subset of subjects (defined in Addendum 2). • HCC confirmed by 2 complimentary imaging modalities, unless confirmed by biopsy. • Biomarkers, including other markers of hepatic fibrosis and/or inflammation, to be tested will include: IgM, c reactive protein (CRP), tumor necrosis factor α (TNF-α), FGF 19, cytokeratin-18 (CK-18) ELF, and Fibroscan (and others as determined during the course of the study). • Clinical outcomes, including individual component of the primary endpoint 	
Clarified and re-ordered bullets for consistency throughout document.
 
Addition of Addendum 2. Reflects addition of a biopsy substudy available to interested sites in Addendum 2.

Section	Original Text (Amendment 3.1, 21 December 2016)	Revised Text (Version 4, 10 May 2017)	Justification for Change						
	
 Endoscopy will be conducted at selected study sites where the device is available to assess for the presence of oesophageal varix/varices at baseline. 	
(where available), liver transplant, and death will be compared to historical controls.
 
 PK of OCA and its conjugates. Endoscopy will be conducted at all study sites where the device is available to assess for the presence of oesophageal varix/varices at baseline. 							

Section 12.1.3 Relationship of Adverse Events to Liver Biopsy
	
Insertion (new section)
	
The Investigator will document her/his opinion of relationship of an AE to liver biopsy using the criteria outlined in Table 9.
 
Table 9: Relationship of Adverse Events to Liver Biopsy
 
  
 Relation ship	Description	
   
 Related	A reaction that follows a reasonable temporal sequence from the liver biopsy; that follows a known or expected response pattern to the liver biopsy.	
 
 Not Related	Any event that does not meet the above criteria.	
  
	Relation ship	Description	Related	A reaction that follows a reasonable temporal sequence from the liver biopsy; that follows a known or expected response pattern to the liver biopsy.	Not Related	Any event that does not meet the above criteria.	
Added with the addition of liver biopsies for the confirmation of progression to cirrhosis.

Relation ship	Description								
Related	A reaction that follows a reasonable temporal sequence from the liver biopsy; that follows a known or expected response pattern to the liver biopsy.								
Not Related	Any event that does not meet the above criteria.								

Section 12.1.5.2 Reporting of Serious Adverse Events
	
[contact] If an SAE is reported by telephone or fax, an SAE Report form must also be completed in the EDC system as soon as the EDC system is accessible.
	
If an SAE is reported by email or fax, an SAE Report form must also be completed in the EDC system as soon as the EDC system is accessible.
	
Updated to align with modified standard safety procedures.
						

Section 12.1.6 Suspected Liver-Related Clinical Outcome Events
	
Section 12.1.5 Given that the liver-related clinical outcome events could also meet the criteria of a SUSAR, which would necessitate unblinding for expedited reporting, the Sponsor will not expeditiously report suspected liver-related clinical outcome events in order to retain the study
	
Section 12.1.6 Given that the liver-related clinical outcome events may also meet the criteria of a SUSAR, but are considered in aggregate as part of the primary endpoint and the DMC reviews of all safety and efficacy data at least quarterly, the Sponsor will not expeditiously report suspected
	
Updated to align with modified standard safety procedures and Sponsor standard language.
						

Section	Original Text (Amendment 3.1, 21 December 2016)	Revised Text (Version 4, 10 May 2017)	Justification for Change
	
blind and preserve the integrity of the clinical outcomes endpoint.
 
The Sponsor will consider the following list of clinical outcome events (MedDRA preferred terms) to be disease related and exempt from expeditious regulatory reporting, but will continue to report them in a non-expeditious manner: death, end-stage liver disease (preferred term: chronic hepatic failure), liver transplant (preferred term: liver transplant), HCC (preferred term: hepatocellular carcinoma), variceal bleeding (preferred term: gastroesophageal variceal haemorrhage), hepatic encephalopathy (preferred term: hepatic encephalopathy), spontaneous bacterial peritonitis (preferred term: peritonitis bacterial), ascites (preferred term: ascites), and histological progression to cirrhosis (preferred term: hepatic cirrhosis).
	
liver related clinical outcome events in order to retain the study blind and preserve the integrity of the clinical outcomes endpoint.
 
The Sponsor will consider the following list of clinical outcome events (MedDRA preferred terms) to be disease related and exempt from expeditious regulatory reporting, but will continue to report them in a nonexpeditious manner: death, end-stage liver disease (preferred term: chronic hepatic failure), liver transplant (preferred term: liver transplant), HCC (preferred term: hepatocellular carcinoma), variceal bleeding (preferred term: gastroesophageal variceal haemorrhage or oesophageal varices haemorrhage), hepatic encephalopathy (preferred term: hepatic encephalopathy), spontaneous bacterial peritonitis (preferred term: peritonitis bacterial), ascites (preferred term: ascites), and histological or clinical progression to cirrhosis (preferred term: hepatic cirrhosis).
	

Section 12.1.8 Notification of Post-Treatment SAEs for Subjects Who Continue in the Study
	
Insertion (new section)
	
Post-treatment SAEs that occur in subjects who remain in the study after investigational product has been discontinued must be reported to the Sponsor within 24 hours by following the instructions provided in Section 12.1.5.2.
 
SAEs that occur in subjects who discontinue investigational product, initiate treatment with commercially available Ocaliva, and remain in the study must be reported to the Sponsor within 24 hours by following the instructions provided in Section 12.1.5.2.
	
Updated to align with modified safety procedures and Sponsor standard language.


Section 12.1.9 Notification of Poststudy SAEs
	
Section 12.1.7 All SAEs that occur within 30 days following the cessation of investigational product, whether or
	
Section 12.1.9 All SAEs that occur within 30 days following discontinuation from the study, whether or not
	
Updated to align with modified safety procedures

Section	Original Text (Amendment 3.1, 21 December 2016)	Revised Text (Version 4, 10 May 2017)	Justification for Change
	
not they are related to the investigational product, must be reported to the Sponsor within 24 hours by following the instructions provided in Section 12.1.4.2.
 
SAEs that occur more than 30 days after a subject has discontinued study medication, and are not considered related to investigational product, must still be reported in the EDC system; however, these events are not required to be reported within 24 hours. At a minimum, the SAE term, event start and end date, severity, relationship to investigational product, action taken with study medication, treatment, outcome, and potential endpoint status need to be recorded in EDC for the SAE. Additional information (e.g. event summary, SAE details) may also be required to be entered, when requested by the Sponsor.
	
they are related to the investigational product, must be reported to the Sponsor within 24 hours by following the instructions provided in Section 12.1.5.2.
	
and Sponsor standard language.

Section 12.2.7 Laboratory Assessments	
The list of laboratory analytes to be tested is shown in Table 10.
	
The list of laboratory analytes to be tested is shown in Table 11, and the normal reference ranges for liver biochemistries are shown in Appendix C.
	
Added per Regulatory Authority request.

Section 13 Statistical Methods	
A statistical analysis plan (SAP), providing details about the specific planned analyses and hypothesis tests, will be prepared and approved by the Sponsor and its designees prior to study database lock, propensity score determination, and unblinding of the double-blind subject treatment assignments.
	
A statistical analysis plan (SAP), providing details about the specific planned analyses and hypothesis tests, will be prepared and approved by the Sponsor and its designees prior to the first interim analysis, propensity score determination, and unblinding of the double-blind subject treatment assignments.
	
Reflects addition of interim analyses to the study protocol.

Section 13.1.1 Analysis Populations	
Insertion
	
 The Per Protocol (PP) Population will include all ITT subjects who do not have any major protocol violations that potentially affect the efficacy conclusion. Treatment assignment will be based on the randomized treatment. 	
The Per Protocol Population will be used to conduct sensitivity analyses for primary and key efficacy endpoints.

Section	Original Text (Amendment 3.1, 21 December 2016)	Revised Text (Version 4, 10 May 2017)	Justification for Change

Section 13.1.1.1 Comparability of Historical Controls
	
Historical controls from both databases will be chosen based on the same study inclusion/exclusion criteria where possible.
	
Historical controls from both databases will be chosen based on the same study inclusion/exclusion criteria. Propensity score matching method will be utilized to select historical controls that match the treated subjects using available covariates. The adequacy of matching will be assessed by statistical methods described under Section 13.1.8.
	
Clarifies the use of propensity scores in the assessment of the historical control population.


Section 13.1.5 Additional Secondary Efficacy Analyses
	
The following secondary efficacy analyses will compare randomized OCA to randomized placebo on using the ITT population:
	
The following time-to-event secondary efficacy analyses will compare OCA versus placebo using the ITT population:
 
 • Progression to cirrhosis • Time to occurrence of HCC 	
Editorial Change Progression to cirrhosis added as secondary endpoint in Version 3.1. HCC has been redefined as a secondary endpoint instead of a component of the primary composite-event endpoint per Regulatory Authority request.

Section 13.1.5.1 Association of Biochemistry with Clinical Outcomes and Clinical Benefit
	
The association between the effect of OCA on ALP and bilirubin and the clinical benefit of OCA will be evaluated by estimating the proportion of net treatment effect on the primary composite endpoint that is explained by each biochemical marker. For each biochemical endpoint, this proportion will be estimated by applying the partial likelihood function to two Cox models that use the same failure time variable, as described in Lin 1997. This analysis will be based on the ITT population. Based on the association between biochemical changes and clinical outcomes described above, clinical benefit of OCA for key subpopulations of interest will be evaluated. This analysis will be further described in the SAP.
	
The association between biochemistry including ALP and bilirubin with clinical outcomes will be assessed and the clinical benefit of OCA using biochemistry as a surrogate endpoint will be evaluated. Detailed analysis will be described in the SAP. Based on the association between biochemical changes and clinical outcomes described above, clinical benefit of OCA using biochemistry as a surrogate endpoint for key subpopulations of interest will be evaluated. This analysis will be further described in the SAP.
	
This analysis will provide additional insight into the connection between surrogate endpoints and clinical outcome events allowing for evaluation of benefit in subpopulations for which the study is not powered.

Section	Original Text (Amendment 3.1, 21 December 2016)	Revised Text (Version 4, 10 May 2017)	Justification for Change

Section 13.1.8 Supportive Analysis
	
In order to address the risks associated with the inclusion of a long-term placebo arm, supportive analyses of the primary endpoint will compare clinical outcomes in the OCA treatment arm to historical controls.
 
By comparing how outcomes differ for treated subjects relative to historical controls, it is possible to estimate the effects of the treatment.
 
Although it might be relatively simple to assign a historical control based on a single observable characteristic, in practice, if the matching process is to successfully mitigate potential bias, it has to be done considering a full range of covariates across which the treatment and historical controls might differ.
 
Only covariates and not outcome variables will be included in the propensity score estimation. Therefore, there is no chance of biasing, to avoid biased results that are in favor of one treatment.
	
In order to address the risks associated with the inclusion of a long-term placebo arm, supportive analyses of the primary endpoint will compare clinical outcomes in the OCA treatment arm to historical controls, which serves as an external control for supportive analysis.
 
By comparing how outcomes differ for treated subjects relative to historical controls, it is possible to estimate the effects of the treatment between the treated subjects and the matched natural history subjects.
 
A full range of covariates across which the treatment and historical controls might differ will be considered to mitigate potential bias.
 
Only covariates and not outcome variables will be included in the propensity score estimation to avoid biased results that are in favor of one treatment.
 
The baseline characteristics between treated and natural history subjects in the matched dataset will be summarized and presented in a tabular format. Statistical methods such as Wilcoxon Rank-Sum test will be used to assess the balance for baseline covariates. The standardized difference and variance ratios for these covariates will also be calculated. In addition, box plots of propensity scores for treated and natural history subjects will be separately presented, to further assess the adequacy of matching.
 
A third-party statistician(s) will perform the propensity score modeling and matching. This
	
Clarifies the use of the historical controls as an external control in supportive analyses of the primary endpoint and clarify the process for selecting the comparator group for the primary efficacy analysis using propensity score analysis.
 
Clarifies the use of the historical controls as an external control in supportive analyses of the primary endpoint and clarify the process for selecting the comparator group for the primary efficacy analysis using propensity score analysis.


Section	Original Text (Amendment 3.1, 21 December 2016)	Revised Text (Version 4, 10 May 2017)	Justification for Change
	
The propensity score quintile will be then be used as the stratification factor in the stratified log rank test to compare randomized OCA-treated subjects in the ITT population and historical controls (Overall Historical Control Population: both the UK-PBC Group and Global PBC Study Group databases) on the following outcomes:
 
 Time to hepatocellular carcinoma 	
third-party statistician(s) will be separate and independent from the statistician(s) who will assess the success of matching and perform efficacy analyses.
 
The propensity score quintile will be then be used as the stratification factor in the stratified log rank test to compare randomized OCA-treated subjects in the ITT population and historical controls (Overall Historical Control Population: both the UK-PBC Group and Global PBC Study Group databases) on the following outcomes:
	

Section 13.1.9 Handling of Dropouts or Missing Data
	
Insertion
	
In addition, the same analyses for primary and key secondary endpoints based on ITT and PP populations will be performed to assess robustness of analysis results. During the conduct of the study, the DMC may recommend refining the missing data strategy to better address the observed pattern of missing data, based on blinded monitoring of the data.
	
Clarification of statistical analyses to address missing data.

Section 13.1.11 Examination of Subgroups
	
The primary and secondary efficacy endpoints will be analyzed for subject subgroups (eg, age, sex, and race) based on the ITT population.
 
Insertion
	
The primary and secondary efficacy endpoints will be analyzed for subject subgroups based on the ITT population.
 
The primary efficacy endpoint will also be assessed across the spectrum of PBC disease stage as defined by Rotterdam criteria (Kuiper 2009)
 
 Early (normal albumin and normal bilirubin) 	
Added per Regulatory Authority request.

Section	Original Text (Amendment 3.1, 21 December 2016)	Revised Text (Version 4, 10 May 2017)	Justification for Change
		
 • Moderate (abnormal albumin or abnormal bilirubin) • Advanced (abnormal albumin and abnormal bilirubin) 
The primary efficacy endpoint will also be assessed for the following clinically relevant subpopulations.
 
 • Monotherapy in patients who are intolerant or non-responsive to UDCA • Elderly patients 
Assuming a strong correlation between biochemistry and clinical outcomes using the total study population (Section 13.1.5.1) is observed, we will further assess the biochemical improvement in relevant subpopulations as applicable (eg, Rotterdam disease severity and monotherapy) and estimate the reduction in risk of clinical outcomes associated with the biochemical improvement.
 
Additional details regarding statistical methods and subgroup definitions will be provided in the SAP.
	
This analysis will provide additional insight into the connection between surrogate endpoints and clinical outcome events allowing for evaluation of benefit in subpopulations for which the study is not powered.

Section 13.1.12 Continuous Monitoring and Interim Analyses
	
Both interim analyses will be pre-specified and will occur after accrual of 50% and 75% of clinical outcome events, respectively.
 
The DMC will review the available efficacy data in conjunction with detailed safety data and other relevant information to recommend continuation, modification, or cessation (for efficacy or utility) of the study beyond each interim analysis.
	
Both interim analyses will be pre-specified and will occur after accrual of 50% (64 events) and 75% (96 events) of clinical outcome events, respectively.
 
The DMC will review the available efficacy data in conjunction with detailed safety data and other relevant information to recommend continuation,
	
Added number of anticipated events.
 
Clarification

Section	Original Text (Amendment 3.1, 21 December 2016)	Revised Text (Version 4, 10 May 2017)	Justification for Change
		modification, or cessation (for efficacy) of the study beyond each interim analysis	

Section 19 List of References
	
 
Insertion
	
Beuers U, Gershwin M, Gish R, et al. Changing nomenclature for PBC: From ‘cirrhosis’ to ‘cholangitis’. Digestive and Liver Disease. 2015a;47(11):924-6.
 
Beuers U, Gershwin M, Gish R, et al. Changing nomenclature for PBC: From ‘cirrhosis’ to ‘cholangitis’. Gastroenterology. 2015b;149(6):1627-9.
 
Beuers U, Gershwin M, Gish R, et al. Changing nomenclature for PBC: From ‘cirrhosis’ to ‘cholangitis’. Hepatology. 2015c;62(5):1620-2.
 
 
	
Additional relevant references were added.

Appendix C Reference Laboratory Values from Central Laboratories
	
Insertion (new appendix)
 
Deletion: Appendix C in Version 3.1 has been deleted. It is now published as Protocol Addendum 2.
	
Appendix containing reference laboratory values from central laboratories added.
	
Added per Regulatory Authority request.

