The covariates and factors collected in the historical databases will be specified in the SAP.

Propensity scores will be estimated first through a logistic regression model with treatment group as the dependent variable and the above covariates/factors as independent variables. Then the stratum boundaries are determined based on the propensity score values for both groups (OCA population and control [historical and randomized placebo]) combined or in the OCA population or historical control group alone. Based on recommendations in the literature, quintiles of the estimated propensity score from the combined group will be used to determine the stratum boundary cut-offs for the different strata.

The baseline characteristics between treated and natural history subjects in the matched dataset will be summarized and presented in a tabular format. Statistical methods such as Wilcoxon Rank-Sum test will be used to assess the balance for baseline covariates. The standardized difference and variance ratios for these covariates will also be calculated. In addition, box plots of propensity scores for treated and natural history subjects will be separately presented, to further assess the adequacy of matching.

A third-party statistician(s) will perform the propensity score modeling and matching. This third-party statistician(s) will be separate and independent from the statistician(s) who will assess the success of matching and perform efficacy analyses. Outcome events collected in the historical database are: death (liver-related and all-cause), liver transplant, HCC, and other. Other is defined as cirrhosis or decompensation such as ascites, variceal bleed, and encephalopathy.

The propensity score quintile will be then be used as the stratification factor in the stratified log rank test to compare randomized OCA-treated subjects in the ITT population and historical controls (Overall Historical Control Population: both the UK-PBC Group and Global PBC Study Group databases) on the following outcomes:

- Time to death (all-cause)
- Time to liver-related death
- Time to liver transplant
- Time to liver transplant or death (all-cause)
- Time to liver transplant or liver-related death

KM estimates of the distribution of the time-to-event will be tabulated and graphed by treatment group. The tabulation will include the KM estimate of the medians and corresponding 95% CIs if the medians can be estimated. The number and percent of subjects censored and with events

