will be presented. The hazard ratio and 95% CI will be determined based on a Cox regression model stratified by randomization strata to estimate the magnitude of the effect.

Sensitivity analyses will be conducted limiting to the separate individual historical control databases, ie, UK-PBC Group and Global PBC Study Group. To evaluate the robustness of the propensity score estimations, additional algorithms and factors may be considered.

Although the study is designed as a placebo-controlled study, the DMC may recommend changes to study conduct based on the pre-specified interim analyses (see [Section 13.1.12](#)), including the potential use of a revised primary efficacy analysis. This analysis would compare all subjects in the OCA population, to all control subjects (randomized placebo and historical controls) on time to liver transplant or death (all-cause), using similar statistical methodology as specified above.

Notably, the planned primary analysis would not be revised without prior agreement with regulatory authorities.

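### Section 13.1.8 gives the judgement on whether the historical-control match succeeded to the same statisticians who run the efficacy analyses, so acceptance of the comparator is not separated from the outcome comparison

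*Protocol*

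**What the plan says.** Section 13.1.8 (Supportive Analysis) gives the propensity modelling and the matching to a third party: "A third-party statistician(s) will perform the propensity score modeling and matching". It adds: "This third-party statistician(s) will be separate and independent from the statistician(s) who will assess the success of matching and perform efficacy analyses". The Version 4 text recorded in Appendix H has the same wording, so the change log and the current text agree.

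The same section names the balance diagnostics: baseline tables, tests such as the Wilcoxon rank-sum, box plots of the scores and, in its words, "The standardized difference and variance ratios for these covariates will also be calculated". It gives the purpose of keeping outcomes out of the score (Appendix H records the Version 4 wording, and Section 13.1.8 carries the same sentence): "Only covariates and not outcome variables will be included in the propensity score estimation to avoid biased results that are in favor of one treatment".

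On the registry side it says: "Outcome events collected in the historical database are: death (liver-related and all-cause), liver transplant, HCC, and other". Alongside the single-database sensitivity analyses it says: "To evaluate the robustness of the propensity score estimations, additional algorithms and factors may be considered".

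Section 13 requires the SAP to be approved before the first interim analysis, before the propensity scores are determined and before unblinding.

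**The concern.** In a matched external comparison, the step that fixes the comparator is the decision that balance is good enough. Until then the match is a proposal. The usual protection is to finish everything up to that decision using covariates only, and to link outcomes afterwards. Section 13.1.8 protects the building of the match and then names the efficacy analysts as the judges of whether it worked.

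Several matches can often be defended on balance alone. If the judges know the outcomes, acceptance can lean, even unintentionally, towards the match with the more favourable result. The reported p-value and confidence interval would make no allowance for that.

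The judgement carries weight. Section 13.1.1 defines each historical control population by comparability that has been demonstrated, so it bears on who is in the control group. Section 5.5.2.3 uses the comparison to address possible bias in the placebo arm, for example from commercial OCA. Section 13.1.8 also foresees that the DMC might recommend a revised primary analysis of liver transplant or death, with randomised placebo and historical subjects together as the control group.

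**Working it through.** The protocol states no figure on this point, so the check is to set out each task, who holds it, and what protects it from outcome knowledge.

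1. **Estimating the score.** Third party; covariates only (13.1.8). Protected.
2. **Forming the match.** Third party (13.1.8). Protected from the efficacy analysts by the stated independence.
3. **Judging whether the match succeeded.** The statistician(s) who also perform the efficacy analyses (13.1.8). The independence sentence puts this task on the efficacy side. The covariates-only rule concerns estimation of the score and does not reach it.
4. **Comparing outcomes.** The same statistician(s) (13.1.8).
5. **Timing.** SAP approval precedes score determination and unblinding (Section 13). This fixes when the plan is written. It does not put acceptance of the match before access to outcomes.

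Tasks 3 and 4 are in the same hands by the protocol's own wording. That is stated outright. Whether outcomes are in view at task 3 is not stated either way. Registry outcomes are already collected in the historical databases, and the protocol does not say when the assessors receive them or the trial outcomes.

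**Worst-case illustration, on assumed inputs only.** Suppose there is no true effect and the most favourable of k acceptable matches is always kept. The expected shift in log HR is about E[min of k] × SE × √(1 − ρ), where ρ is the correlation between the estimates, and E[min] is 0.846 SD below the mean for k = 3 and 1.163 SD below for k = 5.

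- Events split evenly, SE = √(4/events):
  - k = 3, 100 events (SE 0.20), ρ = 0.9: 0.846 × 0.20 × √0.1 = 0.054, HR 0.95.
  - k = 5, 60 events (SE 0.258), ρ = 0.7: 1.163 × 0.258 × √0.3 = 0.165, HR 0.85.
- Uneven split, 40 OCA and 200 control events, SE = √(1/40 + 1/200) = 0.173:
  - The shared OCA arm alone gives ρ = 0.025/0.030 = 0.83. With k = 5: 1.163 × 0.173 × √0.167 = 0.082, HR 0.92.
  - With half the controls also shared, ρ = (0.025 + 0.0025)/0.030 = 0.917. With k = 3: 0.846 × 0.173 × √0.083 = 0.042, HR 0.96.

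None of these event counts, correlations or numbers of matches comes from the protocol.

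**The case against.** A reader might infer that the efficacy statisticians may look at the hazard ratio and then have the match redone. The documents do not support that. Nothing says they hold outcomes when they assess balance, the listed diagnostics are all baseline ones, and any rematch would be the third party's work. Nor do the additional algorithms permit replacing the main match: that sentence concerns robustness and follows directly on the sensitivity analyses. The rule that outcomes stay out of the score is kept.

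A missing lock step or balance limit is also no finding in itself, since the SAP is not shown and may supply both. If it puts balance assessment before outcome linkage, one team doing both tasks in sequence would do little harm.

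The present split has a merit as well: the matcher does not mark its own work.

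Finally, the consequence is limited. The comparison is supportive and sits outside the hierarchy in Section 13.1.10, where further tests are descriptive and exploratory. A revised primary analysis would need prior regulatory agreement.

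All of this stands as a limit on the point. It does not remove the role split, which the protocol itself fixes. A SAP that gave acceptance to the third party would contradict the sentence in Section 13.1.8. The wish for a checker other than the matcher is reasonable, but that checker need not be the efficacy analyst.

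**Conclusion.** The point holds as a misplaced boundary. Section 13.1.8 assigns the judgement on the match to the people who run the outcome comparison, which leaves open a route to outcome-informed acceptance that the protocol does not plan and does not close.

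It affects the supportive OCA-versus-historical comparison, and the revised primary analysis if that were ever adopted. The randomised OCA-placebo log-rank test is untouched.

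No size can be derived from the documents. The hazard ratios of 0.85 to 0.96 assume 3 to 5 acceptable matches, the event counts and correlations shown, and deliberate choice of the most favourable one. They illustrate a worst case and do not forecast bias. The conclusion rests on the wording about roles and not on those figures. The change is worth making because it is cheap and the comparison may be asked to carry more weight later.

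**What to change.** Amend the independence sentence in Section 13.1.8 and align the SAP:

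- Balance (standardised differences, variance ratios, propensity plots) is judged, and acceptance documented, by statistician(s) without access to outcomes. This can be the third party or, if a check independent of the matcher is wanted, another outcome-blind statistician already available.
- The matched set and the propensity strata are locked before registry and trial outcomes are merged.
- The efficacy statisticians receive the locked set. They may report balance but not accept or reject the match.
- Any later algorithm or factor remains a sensitivity analysis.

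The cost is a few lines of text and one task moved to people already engaged. It needs no extra data and no change to the randomised analyses.
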